8.3.5 DEVELOPMENTAL SAFETY UPDATE REPORTS (DSUR)

Developmental Safety Update Reports (DSUR) will be submitted to the Sponsor and Regulatory Authority in accordance with local (MHRA) regulatory requirements.

9. ASSESSMENTS & FOLLOW-UP

Potentially eligible participants will be identified through adverts, mainstream, community and social media. They will be able to request written information and be able to make an appointment for a screening visit for further discussion should they prefer to do this in person.

The Delegation Log will determine which members of the trial team are authorised to conduct the assessments and procedures described in this section.

9.1 Trial Assessment Schedule

The assessments in clinic and online, samples and volumes to be collected are outlined in: Table 2:

Collection of adverse event data must begin from the time that informed consent if given by the participant.

The maximum blood volume drawn from a participant in the EML-Vac trial, who completes 52 weeks of follow-up in the trial period, is approximately 403 mL. These volumes do not include the blood volume that would be required if additional diagnostic tests are needed, or safety tests have to be repeated. The required volumes per visit together with sample collection and processing guidelines are described in detail in the Laboratory Manual.

The visits in the trial assessment schedule are: a screening visit (Visit 1); an enrolment visit which must take place within 8 weeks of the screening visit and is defined as Week 0 (Visit 2); injection visits at Weeks 0 and 12 (Visits 2 and 5); safety visits at Weeks 1, 4, 13, 14, 16, 24 and 36 (Visits 3, 4, 6, 7, 8, 9 and 10) and a final visit at Week 52 (Visit 11). The visit windows are provided in **Table 2**.

Information on vaccine reactions will be solicited directly from participants for one week following each injection using the participant facing tools in the EDC system. Participants will attend a site visit 1 day after each injection.

9.2 Procedures During the Screening Period

Screening will take place as close to the planned enrolment as possible, no longer than 8 weeks before enrolment but allowing time for all relevant laboratory assessment to check participant eligibility.

9.2.1 **INFORMED CONSENT**

Participants will be provided with information about the product, trial design and data collection in writing. They will have the opportunity to ask questions in person or on the phone.

Key points to communicate during the informed consent process:

- That we do not know if the vaccine will prevent Marburg virus, Ebola virus or Lassa virus infection
- That the vaccine does not contain any infectious component and cannot cause symptoms associated with Marburg virus, Ebola virus or Lassa virus infection
- That pregnancy is to be avoided until 18 weeks after the second injection as the safety of the vaccine is not known

If they are happy to proceed, they will be asked to indicate their informed consent in writing prior to answering questions about their health and providing samples for the screening investigations. Laboratory investigations or other screening procedures defined in this protocol that have been performed at the local clinical sites(s) for some other purpose (routine NHS visit, healthy volunteer database screening, other research) may be used for the purpose of screening so long as the date they were performed is within the window period defined in this protocol.

A copy will be provided to the participant and one copy kept in the trial file according to local procedures.

9.2.2 **ELIGIBILITY**

To assess eligibility, demographic information, a past and current medical history, and details of all current medication will be collected on worksheets and transcribed into the EDC system. Details of contraception to assess the risk of pregnancy arising in the participant/their partner will also be collected.

The screening examination will include weight (kg), height (cm), temperature, blood pressure, pulse, oxygen saturation, inspection of the skin to exclude severe eczema and respiratory, cardio-vascular, abdominal and neurological examination. An assessment of cervical, axillary and inguinal lymph nodes will also be undertaken.

Clinical Investigators should carefully assess participants who have pre-existing conditions and consider the maximum severity in the past, the extent of treatment needed to control the condition at the time of screening, and how long the participant has been stable for on their current treatment. If further investigation is required, including an additional ECG, or the Clinical Investigator suspects the need for a change in treatment, the participant should be considered ineligible under exclusion criterion number 2 (see Section 5.3).

9.2.3 **Investigations**

Blood will be collected for analysis of routine parameters and processed in the local NHS laboratories for full blood count and biochemistry. The parameters are listed in a footnote to **Table 2** but additional tests to be conducted at screening are:

- Hepatitis C antibody
- HIV antibody
- Gamma glutaryl transferase
- Urine dipstick for glucose, blood, WBC, nitrite and protein

Volunteers with Grade 1 abnormalities in haematology, biochemistry or urinalysis parameters at the initial screening visit may have the tests repeated once and may enter the trial if the repeat result is normal, at the investigator's discretion. In the event the repeat reveals a new Grade 1 abnormality the volunteer will be considered ineligible.

For female participants of childbearing potential, a pregnancy test will be performed by analysis of a urine sample for Human Chorionic Gonadotrophin (HCG).

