3.1.2 MARBURG VIRUS

The Marburg virus is a highly virulent haemorrhagic fever virus which can lead to Marburg Virus Disease. The Marburg virus spreads though human-to-human transmission following direct contact with blood and other bodily fluids of infected people through broken skin or mucous membranes. The virus can also be transmitted through surfaces and materials such as bedding, and clothes contaminated with these fluids from infected individuals [2].

The disease was first identified following two large outbreaks in Serbia and Germany in 1967. These outbreaks started in laboratories that were carrying out work on African Green Monkeys which had been imported from Uganda. Since 1967 further significant outbreaks of Marburg Virus Disease have been reported in Central and Southern Africa [2].

Between days 5-7, many patients who have been infected by the Marburg Virus develop severe haemorrhagic manifestations, and in cases that are fatal, bleeding from the nose, gums and vagina (in women) is observed. Death occurs between 5-8 days after the onset of symptoms and is preceded by extreme blood loss and shock [2].

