3.1.3 EBOLA VIRUS

The Ebola virus first appeared in 1976, in two simultaneous outbreaks in the Democratic Republic of Congo and South Sudan. The virus takes its name from the Ebola River, a tributary of the Congo River in the Democratic Republic of Congo, where it was first identified [3].

The Ebola virus is a highly virulent haemorrhagic fever virus which can lead to Ebola Virus Disease and Ebola Haemorrhagic Fever in humans and primates. It is thought that the virus may be carried by fruit bats who are unable to become infected. Spread of the virus in humans is through body fluids or through contact with surfaces and materials that have been contaminated with infectious body fluids.

Symptoms manifest between 2 days and 3 weeks post infection of the virus and present as fever, sore throat and muscle pain, followed by vomiting and diarrhoea and reduced liver and kidney function. In some instances, patients will bleed both internally and externally leading to death. Up to 90% of people that will be infected with the Ebola virus will not survive [3].

Currently, there are 2 licensed vaccines to prevent Ebola virus, the 1-dose rVSVAG-ZEBOV-GP (ERVEBO [Merck]) and the 2-dose regimen of Ad26.ZEBOV and MVA-BN-Filo (Zabdeno/Mvabea [Johnson & Johnson]).

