3.1.4 LASSA VIRUS

The Lassa virus is a highly virulent haemorrhagic fever virus which can lead to Lassa Haemorrhagic Fever and is endemic in many West African countries. The virus is spread through contact with the urine or faeces of a multimammate mouse [4], and onward transmission through human-to-human contact. Many people infected with this virus remain asymptomatic. When symptoms present, they include headache, muscle ache, vomiting and chills. The mortality rate of this virus is around 1%, although thought to be 15% in hospitalised patients and death can occur within 2 weeks of infection.

There is no licensed vaccine for Lassa virus, however new vaccine candidates against this virus are currently being developed and tested.

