8.1.2 EXPECTED ADVERSE EVENTS

The safety and reactogenicity of the IMP is expected to be comparable to the safety observed in previous clinical trials conducted where saRNA have been tested with other vaccine antigens in Phase I clinical trials (COVAC1, COVAC Uganda). See summary table 5 below for systemic and local reactions reported in individuals who received a 5 µg dose of LNP-nCoVsaRNA vaccine.

Up to 100% of participants are expected to experience grade 1-2 systemic reactions including fatigue, myalgia, headaches, chills/shivering and arthralgia. Similarly, close to 100% of participants are expected to experience grade 1-2 local reactions, with pain and tenderness/discomfort likely to be the most common local reactions.

Uncommon reactions include high temperature (≥ 38°C), nausea and vomiting, and erythema and induration at site of injection.

Vasovagal syncope (i.e. fainting), may occur in this population of subjects. It will be attempted to minimise the occurrence of this reaction, by allowing the subjects to lie down during administration of vaccine and blood drawings.

Table 5. Adverse Events in participants the COVAC1 clinical trial who received a 5 μg dose of LNP-nCoV-saRNA

		LNP-nCoVsaRNA dose
		5.0 μg N=24
	Any	
	Normal	0 (0.0%)
	Grade 1	8 (33.3%)
	Grade 2	14 (58.3%)
	Grade 3	2 (8.3%)
	Temperature	
	Normal	21 (87.5%)
	Grade 1	2 (8.3%)
	Grade 2	0 (0.0%)
	Grade 3	1 (4.2%)
	Chills/shivering	
	Normal	10 (41.7%)
	Grade 1	11 (45.8%)
	Grade 2	3 (12.5%)
	Myalgia (flu-like general ı	
	Normal	5 (20.8%)
	Grade 1	13 (54.2%)
	Grade 2	6 (25.0%)
	Grade 3	0 (0.0%)
	Arthralgia	
0	Normal	11 (45.8%)
Systemic	Grade 1	9 (37.5%)
	Grade 2	4 (16.7%)
	Grade 3	0 (0.0%)
	Fatigue	
	Normal	3 (12.5%)
	Grade 1	11 (45.8%)
	Grade 2	10 (41.7%)
	Grade 3	0 (0.0%)
	Sidd 0	0 (0.070)
	Headache Normal	2 (9 20/)
	Grade 1	2 (8.3%) 14 (58.3%)
	Grade 2	8 (33.3%)
	Nausea Normal	19 (79.2%)
	Grade 1	5 (20.8%)
	Grade 2	0 (0.0%)
	Grade 3	0 (0.0%)
		(())
	Vomiting	
	Normal	24 (100.0%)
		24 (100.0%) 0 (0.0%)
	Normal Grade 3	0 (0.0%)
	Normal Grade 3 Any Normal	0 (0.0%)
	Normal Grade 3 Any Normal Grade 1	0 (0.0%) 1 (4.2%) 15 (62.5%)
	Normal Grade 3 Any Normal	0 (0.0%)
	Normal Grade 3 Any Normal Grade 1	0 (0.0%) 1 (4.2%) 15 (62.5%)
	Normal Grade 3 Any Normal Grade 1 Grade 2	0 (0.0%) 1 (4.2%) 15 (62.5%) 8 (33.3%)
	Normal Grade 3 Any Normal Grade 1 Grade 2	0 (0.0%) 1 (4.2%) 15 (62.5%)
	Normal Grade 3 Any Normal Grade 1 Grade 2 Pain Normal	0 (0.0%) 1 (4.2%) 15 (62.5%) 8 (33.3%)

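### Section 9.2.1 has volunteers told that the vaccine cannot cause symptoms associated with the three infections, yet the protocol lists several Ebola and Lassa symptoms as vaccine reactions

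*Protocol*

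**What the plan says.** Protocol section 9.2.1 (Informed Consent, under 9.2) gives three key points to communicate to volunteers. The second is that the vaccine has no infectious component and "cannot cause symptoms associated with Marburg virus, Ebola virus or Lassa virus infection".

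The background sections describe the infections:
- Section 3.1.3 says that Ebola symptoms "present as fever, sore throat and muscle pain, followed by vomiting and diarrhoea".
- Section 3.1.4 says of Lassa: "When symptoms present, they include headache, muscle ache, vomiting and chills".
- Section 3.1.2 says that many Marburg patients "develop severe haemorrhagic manifestations" and names no milder symptoms.

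The safety sections describe the vaccine reactions:
- Section 8.1.2: "Up to 100% of participants are expected to experience grade 1-2 systemic reactions including fatigue, myalgia, headaches, chills/shivering and arthralgia". It adds: "Uncommon reactions include high temperature (≥ 38°C), nausea and vomiting".
- Section 3.2.3 includes diarrhoea and sore throat among the uncommon side effects.
- Section 10.2 makes pyrexia, myalgia, headache and chills solicited systemic outcomes.
- The lay summary names headache, temperature and chills as possible general side-effects.

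**The concern.** The consent point is categorical, and what it rules out is symptoms, not infection or disease. A vaccine with no infectious component cannot give anyone Ebola or Lassa. It can still give headache, muscle ache, chills or fever, and the protocol says elsewhere that it does. Staff who follow 9.2.1 as written would tell healthy first-in-human volunteers something that the rest of the protocol contradicts. The volunteers would also be told to expect those same symptoms as side effects. What is at stake is the accuracy and coherence of the consent message.

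**Working it through.** This is mainly a comparison of text. Each symptom that section 3.1.3 or 3.1.4 gives in the sentences quoted above is set against its status as a vaccine reaction.

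| Symptom | Infection (section) | Vaccine reaction (section) |
|---|---|---|
| Muscle pain | Ebola (3.1.3), Lassa (3.1.4) | Expected (8.1.2); solicited (10.2) |
| Headache | Lassa (3.1.4) | Expected (8.1.2); solicited (10.2) |
| Chills | Lassa (3.1.4) | Expected (8.1.2); solicited (10.2) |
| Fever | Ebola (3.1.3) | Uncommon (8.1.2); solicited (10.2) |
| Vomiting | Ebola (3.1.3), Lassa (3.1.4) | Uncommon (8.1.2) |
| Diarrhoea | Ebola (3.1.3) | Uncommon (3.2.3) |
| Sore throat | Ebola (3.1.3) | Uncommon (3.2.3) |

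All seven appear on both sides. None of them is listed for Marburg in section 3.1.2.

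**How common the overlap is.** The only counts in the protocol are in Table 5: 24 recipients of 5 µg of the earlier coronavirus saRNA vaccine.

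*Reproducing the table.* The stated shares without a reaction are headache 2/24 = 8.3%, myalgia 5/24 = 20.8%, chills 10/24 = 41.7% and temperature 21/24 = 87.5%. All four match.

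*Share with a reaction of any grade* = (24 − number normal)/24. The Wilson 95% interval is

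[p + z²/(2n) ± z·√(p(1−p)/n + z²/(4n²))] / (1 + z²/n), with z = 1.96 and n = 24.

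| Symptom | Count | Share | Wilson 95% CI |
|---|---|---|---|
| Headache | 14 + 8 = 22/24 | 91.7% | 74.2% to 97.7% |
| Myalgia | 13 + 6 = 19/24 | 79.2% | 59.5% to 90.8% |
| Chills | 11 + 3 = 14/24 | 58.3% | 38.8% to 75.5% |
| Raised temperature | 2 + 0 + 1 = 3/24 | 12.5% | 4.3% to 31.0% |

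For headache: (0.9167 + 0.0800)/1.1601 = 0.859, and 1.96 × √(0.00318 + 0.00167)/1.1601 = 0.118. This gives 0.742 to 0.977.

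Headache alone means that at least 22 of the 24 had a symptom that section 3.1.4 lists for Lassa. Vomiting was reported by none of the 24, and Table 5 as shown has no rows for diarrhoea or sore throat. The size of the overlap therefore rests on headache, myalgia and chills, with a small contribution from fever.

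**The case against.** The strongest defence is context. The bullet opens with the absence of any infectious component, and the bullet before it is about infection. The natural intent is that the vaccine cannot cause the disease. That is very probably what was meant, but it does not repair the wording. This is a key point to be conveyed to lay volunteers, who should not have to read disease where they are told symptoms.

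Three stronger readings are tempting, and the documents do not support them.

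- *A reader might infer that reactogenicity is being withheld.* It is not. Sections 3.2.3 and 12.2.1 list the expected side effects and say that they will be explained to participants, and the lay summary names several. The three key points in 9.2.1 are not the whole of the consent content.
- *A reader might infer that participants will misattribute, under-report or report late, and so bias the safety outcomes.* Nothing in the protocol shows this. Staff go through the diary with each participant (9.3.3), reactions are solicited directly for a week after each injection (9.1), and site staff check entries one day after injection and at the next visit (9.4). Named symptoms count by onset within 7 days (10.2), and the investigator assigns causality (8.2.3). A participant's own view of the cause does not decide whether a solicited symptom is counted.
- *A reader might turn 91.7% into a forecast of about 37 of the 40 participants (0.917 × 40 = 36.7).* That is too precise. The rate comes from 24 people given another antigen at 5 µg, while the groups here receive 4 to 13 µg in total. The Wilson limits alone span about 30 to 39 of 40 (0.742 × 40 = 29.7; 0.977 × 40 = 39.1).

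Two limits on the overlap also stand: it covers Ebola and Lassa but not Marburg, and section 8.1.2 calls fever uncommon.

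**Conclusion.** The point holds as an internal inconsistency in consent wording, of minor severity. Read as written, the 9.2.1 statement is contradicted by sections 3.1.3 and 3.1.4 set beside 8.1.2, 3.2.3 and 10.2. Most participants can be expected to have at least one symptom that the statement says the vaccine cannot cause. That expectation assumes reactogenicity comparable to the earlier saRNA vaccine, which is the protocol's own expectation in section 8.1.2. The contradiction itself needs no such assumption, because it lies in the text. Whether the information sheet repeats the statement cannot be judged, since the sheet is not shown.

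**What to change.** Reword the bullet in section 9.2.1. It should say that the vaccine contains no infectious component and cannot cause Marburg, Ebola or Lassa infection or disease. It should add that the vaccine may cause short-lived symptoms, for example headache, muscle ache, chills or fever, which can resemble early symptoms of those infections and should be entered in the diary. Check the participant information sheet for the same statement and align it if it is there.

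The cost is one sentence in the protocol, possibly one in the information sheet, and notification to the ethics committee. Design, sample size, outcomes and analysis are unchanged.

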9.3 Procedures at Enrolment

9.3.1 ELIGIBILITY

Study staff will review any new medical conditions or new medications since the screening data were collected and, for female participants, any changes in contraception. Temperature, blood pressure, pulse, oxygen saturation and inspection of the skin will be repeated at the enrolment visit in case anything has changed. Study staff will repeat the other aspects of the physical examination done at the screening visit if symptoms indicate the need for this. All this information will be recorded on the EDC system.

A temperature over 37.5°C would prevent injection on the day. Clinicians should consult the PI/Medical Delegate if there are any Grade 1 (mild) symptoms or signs listed in Table 4.

Blood for immunogenicity testing will be collected. Samples will be sent to the central laboratory at Imperial College London for analysis.

For female participants of childbearing potential, a pregnancy test will be performed by analysis of a urine sample for Human Chorionic Gonadotrophin (HCG) and a negative result will be confirmed before proceeding to enrolment.

9.3.2 **ENROLMENT/RANDOMISATION**

Confirmation of eligibility will depend on entering screening data in the EDC system.

9.3.3 INJECTION

Study staff will draw up the vaccine product (0.5 mL) or placebo (0.5 mL) from the vial and administer it into the deltoid muscle of the participant's choice and record this in the EDC system including the time of injection. All injections should be administered to the same arm.

Following injection participants should remain in clinic for at least 60 minutes, in order to assess and record solicited adverse events within 25-60 minutes following injection. Study staff will go through the detail to be added in the online vaccine diary cards with participants and explain how and when to complete these over the following 7 days.

9.4 Procedures for Assessing Safety

Vaccines are associated with a number of well-characterised local, systemic and laboratory reactions referred to as solicited adverse events (**Table 4**). These adverse events will be purposively collected.

Local and systemic assessments will take place on the day of each injection before the injection, and 25-60 minutes after the injection. **Participants should remain in the clinic for at least one hour after each injection.**

Participants will be asked to complete vaccine diary cards on the EDC system to assist collection and grading of local and systemic adverse events that start within 7 days of the injection. They will be advised to contact trial staff if any events are Grade 3 (severe), and these will be flagged in the EDC system for immediate attention with a view to organising an early visit. Information entered will be checked by staff at site 1 day after each injection and at the next visit.

Blood (~10 mL) for routine safety parameters will be collected at all trial visits. If the total bilirubin is elevated, trial staff will request a result for conjugated bilirubin in order to grade the abnormality and determine any action to be taken with respect to further investigation and interruption to the vaccine schedule.

Vital signs (BP, HR, oxygen saturation and oral temperature) will be measured at every trial visit.

Physical examinations of the injection site, and other body systems if indicated, will be performed on the day of each vaccination, and 1 week after. Symptom-directed physical examinations will be performed at all other follow-up visits.

9.5 Procedures for Assessing Immune Responses

Vaccine immunogenicity will be assessed through collection of blood samples at every post-screening visit and sent to a central laboratory to evaluate serum binding and neutralising antibodies according to the Laboratory Analytic Plan. Neutralisation titre will be determined by Marburg, Ebola and Lassa pseudovirus-based neutralisation assay.

9.5.1 **CELLULAR IMMUNE RESPONSES**

In addition, blood samples will be collected and sent to a central laboratory for processing and to assess B and T cellular responses in gamma interferon ELISpot assays and through flow cytometry using intracellular cytokine staining, according to the Laboratory Analytic Plan.

9.5.2 INNATE IMMUNE RESPONSE

Additional blood samples will be collected to assess serum analysis of the innate response to vaccination. Blood will be taken on the day of each vaccination and 24 hours post each vaccination and processed for serum. These samples will be sent to a central laboratory for processing. Serum will be used to determine soluble markers of innate immune activation such as CXCL10 (IP10) and interferon alpha.

9.6 Other Adverse Events

Other adverse events will be collected through an open question about health at every trial visit. Study staff will record the diagnosis or the symptoms if a diagnosis is not apparent, the date of onset and the date of resolution, if appropriate. If the event is ongoing, it may be appropriate to conduct a symptom-directed examination.

Events should be graded according to the FDA: Toxicity Grading Scale for Healthy Adult and Adolescent Volunteers Enrolled in Preventive Vaccine Clinical Trials, taking account of local laboratory reference ranges. https://www.fda.gov/media/73679/download

